#### 5.2.2 Pharmacokinetics of BMS-986277

All PK analyses will be performed on the Pharmacokinetic population (described in Section 7.3). Refer to Protocol Section 9.5 for the definition of the PK parameters. The following set of pharmacokinetics endpoints will be used for BMS-986277:

- Cmax: maximum observed blood concentration
- AUC(0-T): area under the concentration-time curve from time zero to time of last quantifiable concentration
- AUC(0-8): area under the concentration-time curve from time zero to 8 hours postdose
- AUC(0-48): area under the concentration-time curve from time zero to 48 hours postdose
- AUC(INF): area under the blood concentration-time curve from time zero extrapolated to infinite time
- T-HALF: apparent terminal half-life
- CLT: total body clearance
- Vss: volume of distribution at steady-state
- Vz: volume of distribution of the elimination phase
- C48: blood concentration 48 hours postdose
- Css-avg: average blood concentration over a dosing interval at steady state
- AI AUC: AUC accumulation index
- AI Cmax: Cmax accumulation index
- THALFeff: effective elimination half-life
- Tmax: time of maximum observed blood concentration
- Ctrough: trough observed blood concentrations

# 5.2.3 Immunogenicity of BMS-986277

All immunogenicity analyses will be performed on the Immunogenicity population (described in Section 7.3). Each endpoint will be summarized for BMS-986277 and nivolumab separately, pending availability of evaluable data. Immunogenicity of BMS-986277 are secondary endpoints while immunogenicity of nivolumab are exploratory endpoints and mentioned in Section 5.3.3. The definitions provided here apply to both.

The endpoint for the study is the incidence of anti-drug antibodies (ADA), defined as the proportion of the study population found to have seroconverted or boosted their pre-existing ADA during the study period.

Validated ADA test methods enable characterization of samples into ADA-positive vs ADA-negative. To classify the ADA status of a participant using data from an in vitro test method, each sample from a participant is categorized based on the following definitions:

#### Sample ADA Status:

[figure not shown]
• Baseline ADA-positive sample: ADA is detected in the last sample before initiation of treatment

[figure not shown]
- Baseline ADA-negative sample: ADA is not detected in the last sample before initiation of treatment
- ADA-positive sample: After initiation of treatment, (1) an ADA detected (positive seroconversion) sample in a participant for whom ADA is not detected at baseline, or (2) an ADA detected sample with ADA titer to be at least 4-fold or greater (≥) than baseline positive titer
- ADA-negative sample: After initiation of treatment, ADA not positive sample relative to baseline

Next, using the sample ADA status, participant ADA status is defined as follows:

#### Participant ADA Status:

- Baseline ADA-positive participant: A participant with baseline ADA-positive sample
- **ADA-positive participant**: A participant with at least one ADA positive-sample relative to baseline at any time after initiation of treatment
  - Persistent Positive (PP): ADA-positive sample at 2 or more consecutive timepoints, where the first and last ADA-positive samples are at least 16 weeks apart
  - Not PP-Last Sample Positive: Not persistent positive with ADA-positive sample at the last sampling timepoint
  - Other Positive: Not persistent positive with ADA-negative sample at the last sampling timepoint
- **ADA-negative participant**: A participant with no ADA-positive sample after the initiation of treatment

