### Treatment Arms and Duration:

- Part 1: a monotherapy dose escalation of BMS-986277.
  - Four dose levels:  $3 \times 10^{10}$  viral particles (vp),  $3 \times 10^{11}$  vp,  $1 \times 10^{12}$  vp, and  $3 \times 10^{12}$  vp.
  - 6-week DLT evaluation period to assess safety with multiple injections which may be extended due to dose delays.
  - Dosing for the initial participants into each cohort in Part 1 will be staggered by 7 days to monitor for sentinel events.
  - Participants will receive 2 cycles (Cycle 1: 42 days, Cycle 2: 28 days) of BMS-986277.
- Part 2: a combination dose escalation of BMS-986277 (using the RD from Part 1; up to 2 cycles) in combination with nivolumab (480 mg Q4W; up to 26 cycles).
  - Participants will receive BMS-986277 at the BLRM-RD, or a lower dose than the BLRM-RD from Part 1.
    - ◆ Dosing for the initial participants into each cohort will be staggered by 7 days to monitor for sentinel events.
- Part 3: a 3-cohort expansion.
  - In Cohort 1, participants with low CD8 TILs ( $CD8 < 2\%$ ) will be treated with BMS-986277 (using the RD from Part 2; up to 2 cycles) in combination with nivolumab (480 mg Q4W; up to 26 cycles).
  - In Cohort 2, participants with mid CD8 TILs ( $2\% \leq CD8 < 20\%$ ) will be treated with BMS-986277 (using the RD from Part 2; up to 2 cycles) in combination with nivolumab (480 mg Q4W; up to 26 cycles).
  - In Cohort 3, participants with high CD8 TILs ( $\geq 20\%$ ) will be treated with BMS-986277 monotherapy (using the RD from Part 1; up to 2 cycles) with an option for subsequent nivolumab treatment (480 mg Q4W; up to 26 cycles).

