  - All participants treated with BMS-986277 and nivolumab (Part 2 and Part 3 Cohorts 1-3) will attend at least three safety follow-up visits (see [Table 2-7](#) and [Sections 5.1.5](#) and [5.1.6](#)), and be monitored during long-term follow-up (ie, survival, overall health, and response) for up to 3 years post first dose of study medication (specific durations are specified in [Sections 5.1.7.1](#) and [5.1.7.2](#)).

For all participants, tumor assessments should occur as outlined in [Section 2](#) (Schedule of Activities). Images will be submitted to an imaging core lab for all participants and may be reviewed by Blinded Independent Central Review (BICR) at any time during the study. Treatment decisions will be assessed by the investigator per study design using RECIST v1.1 or PCWG3 criteria.

Clinical progression/deterioration of disease will be monitored throughout the study for all participants.

[figure not shown]
Safety assessments (AEs, PE, vital signs, laboratory safety tests, 12-lead ECGs, cytokine release monitoring, and ECOG performance status) will be evaluated throughout the study treatment and required follow-up visits. Viral shedding and ADA will be monitored at the 30 and 60 day follow-up visits. Additional monitoring may occur at subsequent follow-up visits as clinically indicated in [Table 2-6](#) (participants treated with BMS-986277 monotherapy only [Part 1 and Part 3 Cohort 3]) and [Table 2-7](#) (participants treated with BMS-986277 and nivolumab [Part 2 and Part 3 Cohorts 1-3]). AE monitoring will be continued throughout the study treatment and required follow-up visits as indicated in [Table 2-6](#) and [Table 2-7](#). Concomitant medications will be collected throughout the study treatment (14 days prior to C1D1) and required follow-up visits as indicated in [Table 2-6](#) and [Table 2-7](#).

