### 5.1.5 Safety Follow-up

Participants will enter safety follow-up when the maximum treatment permitted per protocol has been administered (2 cycles of BMS-986277 for participants treated with BMS-986277 monotherapy [Part 1 and Part 3 Cohort 3] or 26 cycles of nivolumab for participants treated with BMS-986277 and nivolumab [Part 2 and Part 3 Cohorts 1-3]) or once the participant discontinues from study treatment (eg, at EOT).

During safety follow-up, all participants will be evaluated for any new and/or ongoing AEs for at least 60 days for participants treated with BMS-986277 monotherapy and 100 days for participants treated with BMS-986277 and nivolumab after the last dose of study treatment. All AEs considered related to study treatment must be followed to resolution, return to baseline or when deemed irreversible as indicated in [Sections 9.2](#) and [9.2.3](#). Although AE reporting is not required following the start of subsequent anti-cancer therapies, assessments at safety follow-up visits should continue and events considered related to study treatment reported. Note that participants treated with BMS-986277 monotherapy (Part 1 and Part 3 Cohort 3) will be required to attend safety follow-up visits 1 and 2. Participants treated with BMS-986277 and nivolumab (Part 2 and Part 3 Cohorts 1-3) will be required to attend all 3 safety follow-up visits.

Safety follow-up visit 1 (FU1) should occur 30 days from the last dose ( $\pm 7$  days) or may be performed on the date of discontinuation. Safety follow-up visit #2 (FU2) occurs approximately 60 days ( $\pm 7$  days) from last dose of study drug. Safety follow-up visit #3 (FU3) occurs approximately 100 days ( $\pm 7$  days) from last dose of study drug. Safety follow-up visits must be conducted in person.

During FU1 and FU2, participants will also be evaluated for viral shedding. If virus is detected during FU2, samples should continue to be collected at least every 30 days until virus is no longer detected.

All participants will be required to complete the safety follow-up visits as indicated in [Table 2-6](#) or [Table 2-7](#) regardless of whether or not they start new anti-cancer treatment, except those participants who withdraw consent for study participation.

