#### 7.1.3.1 BMS-986277 Infusion (Part 1)

In Part 1 (monotherapy dose escalation), four dose levels of BMS-986277 ( $3 \times 10^{10}$  vp,  $3 \times 10^{11}$  vp,  $1 \times 10^{12}$  vp, and  $3 \times 10^{12}$  vp) are planned. Eligible participants will receive an IV infusion of BMS-986277 at the assigned dose, starting at time zero administered directly into the venous access point using a syringe pump on Days 1, 15, 17, and 19 on Cycle 1 and on Days 1, 3, and 5 on Cycle 2. BMS-986277 will be administered over 5 minutes except for the  $3 \times 10^{12}$  vp dose, which will be administered over 15 minutes. Participants will receive a maximum of 2 cycles of treatment (see [Section 7.1.1](#)).

On BMS-986277 dosing days, participants will receive antipyretic prophylaxis predose and postdose (see [Section 7.7.2](#)). This will generally be acetaminophen/paracetamol and/or ibuprofen at a dose and schedule to manage the participant's clinical condition, providing that it follows the prescribing information for the product(s). Other medications, including diphenhydramine and

indomethacin may be used in line with the study site’s standard practice providing they are not excluded concomitant medications (see [Section 7.7.1](#)). Corticosteroid use may be considered under certain circumstances but should be discussed with the Medical Monitor (or designee) prior to initiation.

At the end of the infusion the administration line should be flushed with normal saline to ensure that the full viral dose has been administered. This flush should only use a sufficient amount of saline to flush the line and should not exceed 30 mL.

Participants can receive prophylactic IV hydration after the end of each infusion, unless clinically contraindicated (see [Section 7.7.2](#)). Up to 1 L of normal saline may be administered over 4 hours, adjusted to meet the physiological and clinical requirements of the individual participant (eg, participant body mass index [BMI], concurrent conditions).

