### **7.1.6 Monotherapy Expansion with Option for Subsequent Nivolumab Treatment (Part 3 Cohort 3)**

**Table 7.1.6-1: Selection and Timing of Dose for Part 3 Cohort 3**

Study Treatment	Unit dose strength(s)/ Dosage level(s)	Dosage formulation Frequency of Administration	Route of Administration
BMS-986277	RD a	C1 to C2: D1, D3, and D5 (up to 2 cycles of 28 days each)	IV
Optional: Nivolumab	480 mg	D1 Q4W up to 26 cycles starting at C3	IV

a RD from Part 1.

In Part 3 Cohort 3, participants will receive an IV infusion of BMS-986277 at the RD determined in Part 1, starting at time zero administered directly into the venous access point using a syringe pump on Days 1, 3, 5 of each cycle. BMS-986277 will be administered over 5 minutes except for the  $3 \times 10^{12}$  vp dose, which will be administered over 15 minutes. The RD from Part 1 will be determined as indicated in [Section 7.1.3](#). Participants should begin study treatment within 3 calendar days of treatment assignment.

On BMS-986277 dosing days, participants will receive antipyretic prophylaxis predose and postdose (see [Section 7.7.2](#)). This will generally be acetaminophen/paracetamol and/or ibuprofen at a dose and schedule to manage the participant's clinical condition, providing that it follows the prescribing information for the product(s). Other medications, including diphenhydramine and indomethacin may be used in line with the study site's standard practice providing they are not excluded concomitant medications (see [Section 7.7.1](#)). Corticosteroid use may be considered under certain circumstances but should be discussed with the Medical Monitor (or designee) prior to initiation.

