# **Summary:**

The number (%) of participants with the following ADA responses will be reported by part, dose level, and overall based on the Immunogenicity population for each treatment.

- Baseline ADA-positive
- ADA-positive
  - Persistent Positive (PP)
  - Not PP Last Sample Positive
  - Other Positive
- ADA-negative

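### The SAP's 16-week rule for persistent ADA positivity is longer than the scheduled BMS-986277 ADA sampling in monotherapy (14.1 weeks in Part 1, 11.1 weeks in Part 3 Cohort 3), so that sub-category mostly reflects follow-up length

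*SAP*

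**What the plan says.** SAP Section 5.2.3 (Participant ADA Status) divides ADA-positive participants into three groups: persistent positive, not persistent with a positive last sample, and other positive. Persistence needs positives at two or more consecutive timepoints, "where the first and last ADA-positive samples are at least 16 weeks apart". An ADA-positive participant is "A participant with at least one ADA positive-sample relative to baseline at any time after initiation of treatment", so the C1D1 predose sample is baseline and cannot start the 16-week clock. SAP Section 8.8 tabulates the three groups by part, dose level and overall on the Immunogenicity population. That population needs only a baseline and one post-baseline assessment (SAP Section 7.3).

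For Part 1 the protocol synopsis states "Participants will receive 2 cycles (Cycle 1: 42 days, Cycle 2: 28 days) of BMS-986277", and Section 7.1.3.1 places the infusions on "Days 1, 15, 17, and 19 on Cycle 1 and on Days 1, 3, and 5 on Cycle 2". Cohort 3 has two 28-day virus cycles dosed on Days 1, 3 and 5 (Table 7.1.6-1). On follow-up, Section 5.1 states "Viral shedding and ADA will be monitored at the 30 and 60 day follow-up visits", and Section 5.1.5 states "Safety follow-up visit #2 (FU2) occurs approximately 60 days" from the last dose, with a window of ±7 days. In Table 9.5-1 (Part 1) the first post-baseline ADA sample is C1D8. In Table 9.5-3 (Cohort 3) it is C1D15, because C1D8 carries no ADA sample there.

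**The concern.** The interval that defines persistence is longer than the time over which monotherapy participants are scheduled to be sampled. Someone positive at every scheduled visit would be placed in the not-persistent, last-sample-positive group. The table would show about 0% persistent ADA in Part 1 and in Cohort 3 monotherapy. Nothing in SAP 8.8 separates participants who were observed long enough and were not persistent from those who could not have been observed long enough. In the combination parts the last ADA sample follows the last nivolumab dose, so the category is open to those who stay on nivolumab. A reader comparing parts, or reading the overall row, could take a difference in sampling time for a difference in immunogenicity.

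**Working it through.** The documents state no sampling span, so there is no planned figure to reproduce. The check is calendar arithmetic with C1D1 as day 1. Span = (day of last dose + 60) − day of first post-baseline ADA sample. The threshold is 16 × 7 = 112 days.

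**Nominal schedule, monotherapy**
- Part 1: C2D1 = 42 + 1 = day 43; C2D5 = day 47; FU2 = 47 + 60 = day 107. Span = 107 − 8 = 99 days = 14.1 weeks.
- Part 1, one cycle only (last dose day 19): 19 + 60 − 8 = 71 days = 10.1 weeks.
- Cohort 3 monotherapy: C2D5 = 28 + 5 = day 33; FU2 = day 93. Span = 93 − 15 = 78 days = 11.1 weeks.
- Cohort 3, one cycle only (last dose day 5): 5 + 60 − 15 = 50 days = 7.1 weeks.

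**Part 1 with windows** (C1D8 ±3, C2D1 ±3, FU2 ±7 days; C2D5 within 7 days of C2D1; C1D15 up to +7 days)
- FU2 +7: 106 days = 15.1 weeks.
- Also C1D8 −3: 109 days = 15.6 weeks.
- Also C2D1 +3: C1D8 on day 5, C2D1 on day 46, C2D5 on day 50, FU2 on 50 + 60 + 7 = day 117. Span = 117 − 5 = 112 days = 16.0 weeks.
- Also C2D5 at its 7-day limit (46 + 7 = day 53): 53 + 67 − 5 = 115 days = 16.4 weeks.
- Also a 7-day C1D15 delay that shifts Cycle 2: 122 days = 17.4 weeks.

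Each of these needs a positive already at C1D8. If the first positive is at C1D15 on day 15, the 16.4-week case ends on day 120 and gives 120 − 15 = 105 days = 15.0 weeks. Without windows, a dose delay of 112 − 99 = 13 days or more is needed.

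**Cohort 3 monotherapy with windows:** C1D15 on day 12, C2D1 on day 32, C2D5 on day 39, FU2 on 39 + 67 = day 106. Span = 94 days = 13.4 weeks. If C2D1 is instead given 6 weeks after C1D5 (5 + 42 = day 47) and C2D5 at its limit (day 54), FU2 with its window is day 121 and the span is 121 − 12 = 109 days = 15.6 weeks.

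**Participants who receive nivolumab, nominal schedule, first post-baseline BMS-986277 ADA sample on day 15**

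| Group | Nivolumab doses | Last dose day | Span to FU2 |
|---|---|---|---|
| Part 2, Part 3 Cohorts 1-2 | 2 | 43 | 88 days, 12.6 weeks |
| Part 2, Part 3 Cohorts 1-2 | 3 | 71 | 116 days, 16.6 weeks |
| Part 2, Part 3 Cohorts 1-2 | 4 | 99 | 144 days, 20.6 weeks |
| Cohort 3, sequential nivolumab | 1 | 57 | 102 days, 14.6 weeks |
| Cohort 3, sequential nivolumab | 2 | 85 | 130 days, 18.6 weeks |

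The last dose must fall on or after 15 + 112 − 60 = day 67.

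**The case against.** **Is the category impossible in monotherapy?** A reader might infer a strict zero. The documents do not support that for Part 1, where windows or delays can reach 16.0 to 17.4 weeks. Later samples are also possible. Protocol Section 5.1 allows extra monitoring at later follow-up visits when clinically indicated. The FU2 footnotes to Tables 9.5-1 and 9.5-3 continue sampling at least every 30 days if virus is detected. Section 5.1.5 ties that continuation to viral shedding, so whether it includes ADA is unclear. One extra ADA sample 30 days after FU2 would give 129 days (18.4 weeks) in Part 1 and 108 days (15.4 weeks) in Cohort 3. Near zero on the scheduled visits is the right description.

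**Does this damage the secondary endpoint?** It does not. SAP 5.2.3 defines the endpoint as ADA incidence, and protocol Section 10.3.4 lists only baseline-positive and ADA-positive participants. A continuously positive participant is still counted as ADA-positive, and all samples are listed.

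**Did the cut to two virus cycles cause the mismatch?** That is tempting, because the SAP follows Revised Protocol 03, describes three and up to six virus cycles in Part 1, and has no Cohort 3. No passage says where the 16 weeks came from. The SAP applies the same definitions to nivolumab, whose ADA sampling continues every 16 weeks. The earlier sampling table is not available. If its last ADA sample was 30 days after the last dose, three Part 1 cycles would have spanned only 13.9 weeks; at 60 days, 18.1 weeks.

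**Will the combination parts show more persistent ADA?** No figure supports that, and no between-part ADA comparison is planned. What stands is that a non-zero rate is attainable there and barely attainable in monotherapy, and that the overall row pools the two.

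**Conclusion.** The point holds for the persistence sub-categories and goes no further. On the nominal schedule the monotherapy sampling span falls short of 112 days by 13 days in Part 1 (112 − 99) and by 34 days in Cohort 3 (112 − 78). In participants who receive nivolumab, the category is reachable from about the third dose in Part 2 and Part 3 Cohorts 1-2, and from about the second in Cohort 3 with sequential dosing. Persistent-positive percentages by part and overall therefore depend on follow-up length.

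This rests on FU2 being the last scheduled BMS-986277 ADA sample, on its timing of 60 days from the last dose of any study drug, and on the sampling tables in Revised Protocol 06. It does not rest on any account of how the 16-week rule arose. It should be corrected, but it does not threaten the ADA incidence result.

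**What to change.** When the SAP is reconciled with Revised Protocol 06, amend Sections 5.2.3 and 8.8 as follows.

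- Derive the span from first to last post-baseline ADA sample for each participant.
- Report persistent positivity only among participants whose span is at least 16 weeks, and show that denominator.
- Label other ADA-positive participants *persistence not assessable*, and state that this is expected for nearly all monotherapy participants.

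The cost is SAP wording and one derived flag. No new samples or protocol change are needed, and ADA incidence is reported as before. The drawback is a small or empty denominator for this sub-category in monotherapy. In the combination parts the denominator is selected for longer time on nivolumab, which a table footnote should say.

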# 6.1 Monotherapy Dose Escalation (Part 1)

Dose escalation during the BMS-986277 monotherapy dose escalation (Part 1) will be guided by BLRM employing the Escalation with Overdose Control (EWOC) principle. The BLRM method is fully adaptive, makes use of all the information available at the time of each dose assignment, not just data from the current dose level, and directly addresses the ethical need to control the probability of overdosing. Furthermore, the BLRM uses the knowledge gained from participants treated with enadenotucirev, because BMS-986277 is the genetically modified form of enadenotucirev. The targeted toxicity rate in this study is in the range of [16%, 33%). The boundary is similar to the toxicity boundary used by a rule-based design (ie, 3 + 3 design) in that a minimum is set to 16% (approximately 1 in 6) DLT rate and a maximum at 33% (approximately 2 in 6) DLT rate. The use of the EWOC principle limits the risk of exposing participants in the next cohort to an intolerable dose by ensuring the posterior probability of the DLT rate exceeding 33% at any dose is capped at 25%.

Due to the nature of the dose escalation process, the exact number of participants to be treated at each dose level cannot be precisely determined. The maximum number of participants to be treated is approximately 24. However, simulation studies with various scenarios show that the expected number of DLT evaluable participants is no more than approximately 18 (Protocol Appendix 9).

Approximately 3 participants will be treated at the starting dose levels of BMS-986277. While the BLRM will use DLT information from the DLT period only, clinical assessment will take into consideration the totality of available data, including PK/pharmacodynamics from all treated participants in assigning a dose level for the next cohort of 3 participants. At least 6 DLT-evaluable participants will be treated at a dose level before it can be recommended as the BLRM-recommended dose (BLRM-RD) for BMS-986277 monotherapy.

The BLRM-RD for BMS-986277 monotherapy is the dose that satisfies the following 3 conditions:

- 1) The empirical posterior probability that the "DLT rate of 16% to < 33%" is greater than a prespecified value (ie, 50%);
- 2) This probability needs to be the largest among the dose levels that satisfy the EWOC condition (ie, the probability that the "DLT rate  $\geq$  33%" must be no greater than 35%);

3) A minimum number of participants (ie, 6) was treated at this dose level.

The final recommended dose (RD) for BMS-986277 monotherapy will be based on the recommendations from the BLRM and overall clinical assessment of all available safety, PK, pharmacodynamic, and efficacy data. Lower doses of BMS-986277 may be tested if none of the planned doses are found to be tolerable as monotherapy. Such decisions will be made after discussion and agreement between the investigators and the BMS Medical Monitor (or designee).

